#### **Veliparib Effect on Etoposide Pharmacokinetics Parameters**

For the dose escalation subjects, a linear mixed effects model analysis will be performed for dose normalized  $C_{\max}$ ,  $AUC_{0-24}$  and  $AUC_{\infty}$ , to compare etoposide pharmacokinetics parameters when co-administered with veliparib (Cycle 1 Day 1) relative to etoposide administered alone (Cycle 2 Day 1). For  $C_{\max}$  and AUC, the logarithmic transformation will be used unless the data indicate that the logarithm has significant non-normality. The model will include effects for visit (Cycle 1 Day 1, Cycle 2 Day 1). The within-subject variability will be accounted for utilizing the repeated statement for the effect of visit. Within the repeated measure analysis modeling framework, the null hypothesis of no difference between etoposide in combination with veliparib and etoposide alone will be tested with a significance level of 0.05. The relative bioavailability of etoposide co-administered with veliparib relative to etoposide alone will be estimated. Point estimates and corresponding 90% confidence intervals for the ratio of etoposide co-administered relative to etoposide alone will be provided. The point estimates will be obtained by antilogarithm of the estimate of the difference of the logarithmic means. The 90% confidence intervals will be similarly obtained by antilogarithm of the endpoints of the corresponding confidence intervals for the difference of mean logarithms obtained within the framework of the repeated measure analysis model.

### **8.1.6.3 Missing Values and Model Violations**

All available data will be included in the mixed effect analyses. Data exclusion, if any, will be documented and justification provided.

Normally values of pharmacokinetic variables ( $C_{\max}$ , AUC, etc.) will be determined without replacing missing individual concentration values, simply using the available data, and if necessary doing the analysis with some missing values for a pharmacokinetic variable. However, if a missing individual concentration results in a value of a pharmacokinetic parameter that may be too low or too high to a meaningful degree, the value of the pharmacokinetic parameter will tentatively be considered missing. In this case, a value for the missing individual concentration may be imputed so that an appropriate value of the pharmacokinetic parameter can be included in the analysis. The imputed value will be obtained using appropriate methodology that takes into account the individual characteristics of the subject.

If an outlier is identified and/or a pronounced non-normal probability distribution is observed (after logarithmic transformation for  $C_{\max}$  and AUC), then a non-parametric analysis may also be performed. Such a model violation may be identified by graphical methods, measures of non-normality (e.g., skewness, kurtosis) or other appropriate methods. If the regimens have unequal variances to the extent that conclusions might be affected, then approximate methods that allow for unequal variances will be used.

### **8.1.7 Safety**

Safety analyses will be performed for Phase 1 and Phase 2 separately.

#### **8.1.7.1 Duration of Study Drug**

A summary of the number of days and/or cycles subjects were exposed to study drug will be provided.

#### **8.1.7.2 Adverse Events**

Analyses of adverse events will include only "treatment-emergent" events, i.e., those that have an onset on or after the day of the first dose of study drug (veliparib or placebo). Analyses will not include those that have an onset greater than 30 days after the last dose of study drug.

Treatment-emergent adverse events will be coded and summarized by system organ class and preferred term according to the Medical Dictionary for Regulatory Activities (MedDRA) adverse event coding dictionary. The percentage of subjects experiencing an adverse event at a given NCI CTCAE version 4.0 grade, and relationship to study drug will be provided. For Phase 1, all summaries will be done by dose level. For Phase 2, comparisons of the percentages of subjects experiencing an adverse event between Arm A and Arm C as well as between Arm B and Arm C will be performed using Fisher's exact test.

#### **8.1.7.3 Serious Adverse Events**

Serious adverse events will be summarized using the same methods as adverse events described above in Section [8.1.7.2](#).

#### **8.1.7.4 Deaths**

The number of subject deaths will be summarized 1) for deaths occurring while the subject was still receiving study drug in this study, 2) for deaths occurring off treatment within 30 days after the last dose of study drug, and 3) for all deaths in this study regardless of the number of days after the last dose of study drug.

#### **8.1.7.5 Longitudinal Analyses of Laboratory and Vital Signs Data**

Changes from baseline will be analyzed for each scheduled post-baseline visit and for the final visit for blood chemistry and hematology parameters, as well as urinalysis and vital sign parameters. If more than one measurement exists for a subject on a particular day, an arithmetic average will be calculated. This average will be considered to be that subject's

measurement for that day. Post-baseline measurements more than 30 days after the last dose of randomized study drug will not be included. Subjects that do not have a baseline measurement or do not have any post-baseline measurements will not be included. For Phase 1, changes from baseline will be analyzed by dose level at each scheduled visit. For Phase 2, comparisons of the differences in mean changes from baseline between Arm A and Arm C as well as between Arm B and Arm C will be made using ANCOVA with treatment group as the factor and baseline as a covariate.

#### **8.1.7.6 Analyses of Laboratory Data Using NCI CTCAE**

Where applicable, blood chemistry and hematology determinations will be categorized according to NCI CTCAE version 4.0 grades, and shifts from baseline NCI CTCAE version 4.0 grades to maximum and final post-baseline grades will be assessed. The baseline and final grades will be defined respectively as the grade of the last measurement collected prior to the first dose of study drug, and as the grade of the last post-baseline measurement collected no more than 30 days after the last dose of study drug. If multiple values are available for a post-baseline measurement, then the value with the highest NCI CTCAE grade will be used in the assessment of shift. Comparisons of the number of subjects experiencing a shift from baseline grades of 0 to 2 or no grade to maximum post-baseline grades of 3 to 4, and from baseline grades of 0 to 2 or no grade to final post-baseline grades of 3 to 4 between Arm A and Arm C as well as between Arm B and Arm C will be performed using Fisher's exact tests. Additional analyses including all measurements collected, regardless of the number of days after the last dose of study drug, will be performed.

Detailed listings of data for subjects experiencing NCI CTCAE Grade 3 to 4 blood chemistry and hematology values will be provided. All measurements collected, regardless of the number of days after the last dose of study drug, will be included in these listings.

#### **8.1.7.7 Analyses of Vital Signs Using Criteria for Potentially Clinically Significant Vital Sign Values**

Detailed listings of data for subjects experiencing potentially clinically significant vital sign values according to the AbbVie-defined criteria for vital sign values will be provided. All measurements collected, regardless of the number of days after the last dose of study drug, will be included in these listings.

#### **8.1.8 Timing of Efficacy Analyses and Safety Evaluations**

When the 126th PFS event is observed, all efficacy and safety data as of this time will be retrieved and entered into the clinical database prior to breaking the study blind. When the data collection is completed and reviewed for completeness and all data management quality assurance (QA) and quality control (QC) procedures are performed, the study blind will be broken and clinical database data will be extracted for documentation and statistical analyses of the efficacy and safety data.

Overall survival will be collected on all subjects. After all survival data have been collected and entered into the clinical database, the clinical database will be extracted again for documentation and a "Final OS Analysis" will be performed on this dataset.

#### **8.1.9 Data Monitoring Committee (DMC)**

A safety DMC will be set up for the Phase 2 portion of the study to review the aggregate unblinded safety data. The initial safety DMC review will occur once the first 30 Phase 2 subjects complete combination treatment. Based on this initial safety DMC review, the frequency of subsequent safety DMC reviews will be determined. However, the initial safety DMC review may occur sooner: if the observed rate of DLT-like events in the aggregate blinded safety review of the first 15 Phase 2 subjects exceeds the rate observed in the MTD/RPTD cohort by more than 10%, the safety DMC will convene immediately to review the aggregate unblinded safety data. The details of the safety DMC setup and procedure will be outlined in a separate document.

The DMC will not evaluate efficacy data.

## **8.2 Determination of Sample Size**

### **Phase 1 Dose Escalation**

The number of subjects required for dose escalation portion will depend upon the toxicities observed as the trial progresses.

### **Phase 2 Randomized Double-Blind**

Assuming a median PFS of 5.5 months for placebo in combination with carboplatin and etoposide followed by placebo monotherapy (Arm C) and a hazard ratio of 0.63 for veliparib in combination with carboplatin and etoposide followed by veliparib monotherapy (Arm A) versus Arm C, a total of 85 PFS events will provide an least 80% power to detect a statistically significant difference between Arm A and Arm C at a one-sided  $\alpha = 0.1$ . Further assuming a hazard ratio of 0.75 for veliparib in combination with carboplatin and etoposide followed by placebo monotherapy (Arm B) versus Arm C, a total of 126 PFS events will be observed across all three arms at the time when 85 PFS events are observed for Arm A and Arm C combined. A total of approximately 180 subjects (60 subjects per treatment arm) will be enrolled into the study to obtain the 126 PFS events.

## **8.3 Randomization Methods**

All subjects in the Phase 2 portion of the study will be randomized using an IRT system. Before the study is initiated, directions for the IRT will be provided to each site. The site will contact the IRT to obtain a Screening (subject) number once the subject has signed the informed consent and a study-specific procedure has been performed (i.e., central laboratory samples drawn). Once the Screening number is assigned, if the subject is not randomized into the study, the reason for screen failure will be documented in the source document and in the eCRF. For others, the site will access the system and a unique randomization number will be provided.

The IRT will randomize subjects in a 1:1:1 ratio to one of the treatment arms as follows:

- Arm A: veliparib in combination with carboplatin/etoposide followed by veliparib monotherapy
- Arm B: veliparib in combination with carboplatin/etoposide followed by placebo monotherapy
- Arm C: placebo in combination with carboplatin/etoposide followed by placebo monotherapy

Subject randomization will be stratified by baseline LDH ( $\leq$  ULN versus  $>$  ULN) and gender. The stratification factors used for the randomization should be the last values on or prior to the date of randomization and should be consistent with those on the eCRF.

A bottle number randomization schedule and a subject randomization schedule will be generated by the Clinical Statistics Department at AbbVie prior to the start of the study. A copy of all randomization schedules will be kept by the Clinical Statistics Department at AbbVie and a copy will be forwarded to the IRT vendor.

## **9.0 Ethics**

### **9.1 Independent Ethics Committee (IEC) or Institutional Review Board (IRB)**

Good Clinical Practice (GCP) requires that the clinical protocol, any protocol amendments, the Investigator's Brochure, the informed consent and all other forms of subject information related to the study (e.g., advertisements used to recruit subjects) and any other necessary documents be reviewed by an IEC/IRB. The IEC/IRB will review the ethical, scientific and medical appropriateness of the study before it is conducted. IEC/IRB approval of the protocol, informed consent and subject information and/or advertising, as relevant, will be obtained prior to the authorization of drug shipment to a study site.

Any amendments to the protocol will require IEC/IRB approval prior to implementation of any changes made to the study design. The investigator will be required to submit, maintain and archive study essential documents according to ICH GCP.

Serious adverse events that meet the reporting criteria, as dictated by local regulations, will be reported to both responsible Ethics Committees and Regulatory Agencies as required by local regulations. During the conduct of the study, the investigator should promptly provide written reports (e.g., ICH Expedited Reports or any additional reports required by local regulations) to the IEC/IRB of any changes that affect the conduct of the study and/or increase the risk to subjects. Written documentation of the submission to the IEC/IRB should also be provided to AbbVie.

## **9.2 Ethical Conduct of the Study**

The study will be conducted in accordance with the protocol, International Conference on Harmonization (ICH) GCP guidelines, applicable regulations and guidelines governing clinical study conduct and ethical principles that have their origin in the Declaration of Helsinki. Responsibilities of the clinical investigator are specified in [Appendix A](#).

## **9.3 Subject Information and Consent**

The investigator or his/her representative will explain the nature of the study to the subject, and answer all questions regarding this study. Prior to any study-related screening procedures being performed on the subject, the informed consent statement will be reviewed and signed and dated by the subject, the person who administered the informed consent, and any other signatories according to local requirements. A copy of the informed consent form will be given to the subject and the original will be placed in the subject's medical record. An entry must also be made in the subject's dated source documents to confirm that informed consent was obtained prior to any study-related procedures and that the subject received a signed copy.

The investigator or his/her representative will explain the nature of the study to the subject, and answer all questions regarding this study. Prior to any study-related screening procedures being performed on the subject, the informed consent statement will be reviewed and signed and dated by the subject, the person who administered the informed consent, and any other signatories according to local requirements. A copy of the informed consent form will be given to the subject and the original will be placed in

the subject's medical record. An entry must also be made in the subject's dated source documents to confirm that informed consent was obtained prior to any study-related procedures and that the subject received a signed copy.

Pharmacogenetic analysis will only be performed if the subject has voluntarily signed and dated a separate pharmacogenetic informed consent form, approved by an IRB/IEC, after the nature of the testing has been explained and the subject has had the opportunity to ask questions. The subject must provide consent specific to pharmacogenetic testing before the pharmacogenetic testing is performed. If the subject does not consent to the pharmacogenetic testing it will not impact the subject's participation in the study.

## **10.0 Source Documents and Case Report Form Completion**

### **10.1 Source Documents**

Source documents are defined as original documents, data and records. This may include hospital records, clinical and office charts, laboratory data/information, subjects' diaries or evaluation checklists, pharmacy dispensing and other records, recorded data from automated instruments, microfiches, photographic negatives, microfilm or magnetic media, and/or x-rays. Data collected during this study must be recorded on the appropriate source documents.

The investigator(s)/institution(s) will permit study-related monitoring, audits, IEC/IRB review, and regulatory inspection(s), providing direct access to source data documents.

### **10.2 Case Report Forms**

Case report forms (CRF) must be completed for each subject screened/enrolled in this study. These forms will be used to transmit information collected during the study to AbbVie and regulatory authorities, as applicable. The CRF data for this study are being collected with an electronic data capture (EDC) system called Rave® provided by the technology vendor Medidata Solutions Incorporated, NY, USA. The EDC system and the study specific electronic case report forms (eCRFs) will comply with Title 21 CFR

Part 11. The documentation related to the validation of the EDC system is available through the vendor, Medidata, while the validation of the study specific eCRFs will be conducted by AbbVie and will be maintained in the Trial Master File at AbbVie.

The investigator will document subject data in his/her own subject files. These subject files will serve as source data for the study. All eCRF data required by this protocol will be recorded by investigative site personnel in the EDC system. All data entered into the eCRF will be supported by source documentation.

The investigator or an authorized member of the investigator's staff will make any necessary corrections to the eCRF. All change information, including the date and person performing the corrections, will be available via the audit trail, which is part of the EDC system. For any correction, a reason for the alteration will be provided. The eCRFs will be reviewed periodically for completeness, legibility, and acceptability by AbbVie personnel (or their representatives). AbbVie (or their representatives) will also be allowed access to all source documents pertinent to the study in order to verify eCRF entries. The principal investigator will review the eCRFs for completeness and accuracy and provide his or her electronic signature and date to eCRFs as evidence thereof.

Medidata will provide access to the EDC system for the duration of the trial through a password-protected method of internet access. Such access will be removed from investigator sites at the end of the site's participation in the study. Data from the EDC system will be archived on appropriate data media (CD-ROM, etc.) and provided to the investigator at that time as a durable record of the site's eCRF data. It will be possible for the investigator to make paper printouts from that media.

## **11.0 Data Quality Assurance**

Computer logic and manual checks will be created to identify items such as inconsistent study dates. Any necessary corrections will be made to the eCRF.

## **12.0 Use of Information**

All information concerning veliparib and AbbVie operations, such as AbbVie patent applications, formulas, manufacturing processes, basic scientific data, or formulation information, supplied by AbbVie and not previously published is considered confidential information.

The information developed during the conduct of this clinical study is also considered confidential and will be used by AbbVie in connection with the development of veliparib. This information may be disclosed as deemed necessary by AbbVie to other clinical investigators, other pharmaceutical companies, and to governmental agencies. To allow for the use of the information derived from this clinical study and to ensure complete and thorough analysis, the investigator is obligated to provide AbbVie with complete test results and all data developed in this study and to provide direct access to source data/documents for study-related monitoring, audits, IEC/IRB review and regulatory inspection.

This confidential information shall remain the sole property of AbbVie, shall not be disclosed to others without the written consent of AbbVie, and shall not be used except in the performance of this study.

The investigator will maintain a confidential subject identification code list of all subjects enrolled in the study (by name and subject number). This list will be maintained at the site and will not be retrieved by AbbVie.

Any pharmacogenetic research that may be done using DNA samples from this study will be experimental in nature and the results will not be suitable for clinical decision-making or patient management. Hence, neither the investigator, the subject, nor the subject's physician (if different than the investigator) will be informed of individual subject pharmacogenetic results, should analyses be performed, nor will anyone not directly involved in this research. Correspondingly, genetic researchers will have no access to subject identifiers. Individual results will not be reported to anyone not directly involved

in this research other than for regulatory purposes. Aggregate pharmacogenetic information from this study may be used in scientific publications or presented at medical conventions. Pharmacogenetic information will be published or presented only in a way that does not identify any individual subject.

### **13.0 Completion of the Study**

The investigator will conduct the study in compliance with the protocol and complete the study within the timeframe specified in the contract between the investigator and AbbVie. Continuation of this study beyond this date must be mutually agreed upon in writing by both the investigator and AbbVie. The investigator will provide a final report to the IEC/IRB following conclusion of the study, and will forward a copy of this report to AbbVie or their representative.

The investigator must retain any records related to the study according to local requirements. If the investigator is not able to retain the records, he/she must notify AbbVie to arrange alternative archiving options.

AbbVie will select the signatory investigator from the investigators who participate in the study. Selection criteria for this investigator will include level of participation as well as significant knowledge of the clinical research, investigational drug and study protocol. The signatory investigator for the study will review and sign the final study report in accordance with the European Medicines Agency (EMA Guidance on Investigator's Signature for Study Reports).

The end-of-study is defined as the date of the last subject's last on-site visit. The sponsor may also end the study upon confirmation that the primary endpoint was statistically met.

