### **Survival Follow-Up (Phase 2 Only)**

All discontinued subjects will have survival information collected via electronic data capture (EDC) at two month intervals (or as requested by sponsor to support data analysis) after the subject discontinues the study and continuing until the endpoint of death, the subject has become lost to follow-up, or AbbVie terminates the study.

All subjects will be followed for survival information (i.e., the date and cause of death or last known alive date if not deceased) unless the subject requests to be withdrawn specifically from study survival follow-up; this request must be documented in the subject's medical record and signed by the Investigator.

If known, post treatment anti-cancer therapies, dates of initiation, and end dates will be collected.

If the subject withdraws from survival follow-up, the study staff may use a public information source (such as county records) to obtain information about survival status only, as appropriate per local regulations.

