## 10.2 Testing Hierarchy

This is a single primary efficacy endpoint (PFS, Arm A vs Arm C) study. Survival data (a total of approximately 136 death events targeted across all three treatment arms) will not be mature at the PFS primary analysis time, thus OS analysis at the time of PFS primary analysis will be considered as an interim analysis. If statistical test is significant (one-sided P value  $\leq 0.1$ ) for the primary efficacy endpoint, then the fixed sequence testing procedure will be performed with a significance level of 0.1 (one-sided) for key secondary efficacy endpoints sequentially. If primary PFS (Arm A vs. Arm C) is not significant, then statistical significance will not be declared for any of the secondary efficacy endpoints.

Hierarchical ranking and alpha spending for primary and each secondary endpoint at the time of PFS primary analysis and OS primary analysis is presented in [Table 5](#).

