**Table 5. Alpha-spending Boundary (One-sided p-value) for Each Ranked Endpoint**

Endpoint	Timing	
	PFS Primary Analysis (approximately 126 PFS events across all 3 arms)	OS Primary Analysis (approximately 136 deaths across all 3 arms)
PFS (A vs C)	0.1	NA
OS (A vs C)	0.0001 (administrative purpose)	0.1
PFS (B vs C)*	0.1	
OS (B vs C)	0.0001 (administrative purpose)	0.1
ORR (A vs C)*	0.1	
ORR (B vs C)*	0.1	

(A, B, and C correspond to the three treatment arms, respectively.)

\* Analysis sets for these three tests are the same as PFS (A vs C).

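### Protocol 13.0 lets the sponsor end the study once PFS is met, which conflicts with the planned OS test at about 136 deaths and, if used, would leave OS and the four tests ranked below it almost no chance

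*Protocol*

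**What the plan says.** Protocol 13.0 closes with two sentences. The first sets the formal end: "The end-of-study is defined as the date of the last subject's last on-site visit". The second adds an option: "The sponsor may also end the study upon confirmation that the primary endpoint was statistically met". Neither mentions survival follow-up.

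Protocol 5.3.1.1 (Survival Follow-Up, Phase 2 Only) has survival status collected by EDC every two months, "after the subject discontinues the study and continuing until the endpoint of death, the subject has become lost to follow-up, or AbbVie terminates the study". Protocol 5.4.1 repeats this, and Table 8 note n adds withdrawal of consent for survival follow-up.

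Protocol 8.1.8 plans a Final OS Analysis. Its timing is "After all survival data have been collected and entered into the clinical database", with no number of deaths and no date.

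SAP 10.2 states that survival data will not be mature at the PFS analysis and that "OS analysis at the time of PFS primary analysis will be considered as an interim analysis". If PFS (A vs C) is not significant, "then statistical significance will not be declared for any of the secondary efficacy endpoints". If it is significant, the secondary endpoints are tested in fixed sequence at one-sided 0.1. Table 5 lists the order: PFS (A vs C), OS (A vs C), PFS (B vs C), OS (B vs C), ORR (A vs C), ORR (B vs C). Each OS comparison gets 0.0001 at the PFS analysis, marked as administrative, and 0.1 at about 136 deaths across the three arms. SAP 12.0 gives the September 2018 cutoff but no trigger for the OS primary analysis.

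**The concern.** OS has a formal role only when PFS (A vs C) succeeds, and that is exactly when 13.0 allows the study to end. No text says which provision prevails. The choice would be made after the blind is broken and after the interim OS look, so whether the OS test at 0.1 ever takes place could depend on results already seen.

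More than OS (A vs C) is at stake. It is second in the sequence and gates four other tests. PFS (B vs C) and both ORR comparisons could have their data complete at the PFS analysis and still not be claimable, because the endpoint above them had been left with the 0.0001 look alone.

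**Working it through.** **1. Reproduce the plan's own figure.** Inputs from Protocol 8.2 and SAP 4.3: HR 0.63, one-sided α = 0.1, power 80%, 1:1 comparison. Schoenfeld: d = 4(z₀.₉₀ + z₀.₈₀)² / (ln 0.63)² = 84.47, rounded up to 85. Power with 85 events is 80.2%. The plan's 85 is confirmed, so the same formula is used for OS below. The 136 deaths cannot be reproduced, because neither document gives an OS hazard ratio or OS power.

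**2. Deaths available at the 126th PFS event.**
- From the documents: 60 subjects per arm; Arm C median PFS 5.5 months; PFS HR 0.63 (A) and 0.75 (B), giving exponential medians of 5.5/0.63 = 8.7 and 5.5/0.75 = 7.3 months.
- Assumed: uniform accrual over R = 10 to 22 months; no dropout; exponential OS with Arm C median 9 to 11 months (the range in Protocol 3.1, background text only); OS HR either 0.63 (A) and 0.75 (B), or 1.0 in both.

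The expected fraction with an event by month T > R is 1 − [e^(−λ(T−R)) − e^(−λT)]/(λR), with λ = ln 2/median. T is solved for 126 PFS events, and deaths are then read at that T. The extremes are:

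| Accrual (months) | Arm C median OS (months) | OS HR, A / B | Month of 126th PFS event | Deaths, all arms | Deaths, A and C | Month of 136 deaths | Extra months |
|---|---|---|---|---|---|---|---|
| 10 | 11 | 0.63 / 0.75 | 17.7 | 83 | 56 | 34.1 | 16 |
| 22 | 9 | 0.63 / 0.75 | 25.2 | 98 | 66 | 35.9 | 11 |
| 10 | 11 | 1.0 / 1.0 | 17.7 | 98 | 65 | 27.6 | 10 |
| 22 | 9 | 1.0 / 1.0 | 25.2 | 112 | 75 | 30.8 | 6 |

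So 83–112 deaths, or 61–82% of 136, which agrees with the SAP's statement that OS will be immature.

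**3. Power for OS (A vs C).** Power = Φ(|ln HR|·√d/2 − z₁₋α), with z = 3.719 for α = 0.0001 and 1.282 for α = 0.1. At 136 deaths about two thirds fall in A and C: 136 × 2/3 = 90.7, taken as 91.

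| A and C deaths | α (one-sided) | HR 0.63 | HR 0.75 |
|---|---|---|---|
| 56 | 0.0001 | Φ(1.729 − 3.719) = 2.3% | 0.4% |
| 75 | 0.0001 | Φ(2.001 − 3.719) = 4.3% | 0.7% |
| 91 | 0.1 | Φ(2.204 − 1.282) = 82.2% | 53.6% |

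The 75-death row is generous at HR 0.63, since that many deaths arise in the model only with no OS effect. Pairing HR 0.63 with its own 56–66 deaths gives 2.3–3.3%. To pass at 0.0001 the observed HR would have to be at or below exp(−2 × 3.719/√d), which is 0.37 at 56 deaths and 0.42 at 75.

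**The case against.** The strongest reply is that the documents already show the intention to complete OS. Protocol 8.1.8 promises a Final OS Analysis, the later SAP sets about 136 deaths for it, and 13.0 says only that the sponsor may stop. This is a Phase 2 trial at one-sided 0.1, and OS hazard ratios and intervals will be reported whatever happens. All of that stands. The point is an unresolved conflict between provisions, and what is at risk is the formal test, not the description of OS.

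Three stronger readings are tempting and are not supported.

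- A reader might infer that the on-site-visit definition itself cuts off OS. It does not. Survival contacts continue off-site after a subject leaves the study, and the last on-site visit is not among the listed reasons for stopping them. The definition only leaves those contacts outside the formal end of study.
- A reader might infer that every later test is blocked outright. OS could in principle pass at 0.0001, so the block is near-total, not absolute.
- A reader might infer that stopping early certainly forfeits the 0.1. The SAP does not say what would happen to that alpha if fewer than 136 deaths were available. At 0.1, the 56–75 A and C deaths would give about 67–76% power at HR 0.63. The most that can be said is that 0.0001 is the only boundary given for that time.

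It is also fair that confirming the PFS result takes time, and deaths accrue meanwhile: about 9–10 in two months across all arms in this model. That changes little. At 80 A and C deaths, power at 0.0001 and HR 0.63 is still only 4.9%.

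**Conclusion.** The concern holds as a conflict that should be reconciled. Protocol 13.0 gives an unrestricted, post-unblinding option to stop, and using it would end the follow-up on which the second-ranked test depends. If it were used at the PFS analysis and OS were judged at the stated boundary, power at an assumed OS HR of 0.63 would be about 2–4% instead of about 82%, and the four lower-ranked tests would almost never be reached. At HR 0.75 the contrast is under 1% against about 54%.

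The OS hazard ratios, control median OS, accrual length and absence of dropout are assumptions; the documents supply none of them as design inputs. The conclusion does not change across the ranges shown. The sample size and the PFS event counts are not in question.

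**What to change.** In Protocol 13.0, state that meeting the primary endpoint does not end survival follow-up before the OS primary analysis at about 136 deaths. Termination for safety or reasonable cause under 5.4.2 is unaffected. Put the same death-count trigger in Protocol 8.1.8 and SAP 12.0. Simply deleting the sentence in 13.0 would be weaker, because neither section would yet say when the OS analysis is due. As a secondary tidy-up, extend the end-of-study definition to the last survival contact.

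Sample size, PFS events and alpha do not change. The cost is about 6–16 further months of two-monthly survival contacts after the PFS analysis: nearer 6–10 if there is no OS effect, and nearer 11–16 with OS HRs of 0.63 and 0.75. Table 5 already implies that follow-up.
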